7.2.3 Clinical Outcome Assessments

ICU length of stay will be calculated in days from time = 0 to the earlier of ICU discharge or death. Any re-admissions to the ICU during the hospital stay will add days to ICU length of stay. Hospital length of stay will be calculated in days from time = 0 until the earlier of hospital discharge or death. A follow up at D28 and D60 will further evaluate the stated clinical outcomes.

Concomitant medications and adverse events will continue to be monitored and recorded in the CRF for the duration of the participant's hospital stay.

See the Schedule of Procedures in Appendix A for further details.

8.0 PROTOCOL DEVIATIONS

Protocol deviations will be recorded and reported to the local IRB. If the protocol deviation has placed the participant at increased risk, it will be reported to the safety officer and the IRB within 24 hours. If the protocol deviation has resulted in no increased risk, the event will be reported to the IRB at continuing review.

9.0 ADVERSE EVENTS

Investigators will determine daily if any clinical adverse experiences occur during the period from enrollment to 48 hours after study drug termination. Most data normally collected as part of a clinical study to guarantee patient safety and determine efficacy is obtained as part of normal clinical care of patients in the hospital or ICU. Examples include arterial blood gases, electrolytes, liver function tests, hemograms, and chest radiographs. All available clinical data, including radiographs, laboratory values, vital signs, exam findings, and clinical impressions from the primary team, will be monitored for adverse events. The investigator will evaluate any changes in laboratory values and physical signs and will

determine if the change is clinically important and different from what is expected during treatment of patients with acute hypoxemic respiratory failure. If clinically important and unexpected adverse experiences occur, they will be recorded on the adverse event case report form. Investigators will report all serious and unexpected adverse events to the safety officer and the local IRB in a timely manner. All adverse events that are deemed non-serious and or not unexpected will be reported to the IRB annually at continuing review.

Patients will be closely monitored in a hospital or ICU setting. This will allow for prompt treatment of any adverse event that is suspected to be related to study drug, in which case the safety monitor will be notified and will evaluate the situation. In such an instance study drug infusion will be withheld until the event is evaluated and a decision has been made whether the infusion will be restarted or permanently discontinued.

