9.1 Adverse Events

An adverse event is defined as any untoward medical occurrence in a patient or clinical investigation participant administered a pharmaceutical product that does not necessarily have to have a causal relationship with this treatment. An adverse event therefore can be any unfavorable and unintended sign (e.g., abnormal laboratory finding), symptom, or disease temporally associated with the use of an investigational product, whether or not the incident is considered to be related to the investigational product. Incidences of hypotension, hepatitis (i.e. elevation of liver enzymes), and injection site reactions will be systematically collected and will be considered adverse events.

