9.2 Clinically Significant Laboratory Values

Any change in laboratory values will be evaluated. If a laboratory abnormality is new from baseline and thought to be clinically significant, it is considered a laboratory adverse event. However, if the laboratory value abnormality is consistent with a current diagnosis, it will not necessarily be considered an adverse event. Changes in laboratory values will only be considered adverse events if they are judged to be clinically significant (if some action or intervention is required or if the investigator judges the change to be beyond the range of normal fluctuation). Due to most of the urea cycle enzymes being hepatically located, elevation of liver enzymes will be systematically collected.

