### **Statistical Method for the Secondary Safety Endpoint (Adverse events)**

All reported adverse events will be tabulated and categorized by level of severity and reported by treatment groups. Adverse events will be evaluated further where causality is attributed as suspect.

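### Protocol 9.0 limits adverse event form entry to important, unexpected experiences, against the 9.1 definition, so some expected events may be missing from a secondary safety endpoint

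*Protocol*

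**What the plan says.** Protocol 9.0 has the investigator review changes in laboratory values and physical signs and "determine if the change is clinically important and different from what is expected during treatment of patients with acute hypoxemic respiratory failure". The rule for the form follows: "If clinically important and unexpected adverse experiences occur, they will be recorded on the adverse event case report form". Later in the same section: "All adverse events that are deemed non-serious and or not unexpected will be reported to the IRB annually at continuing review".

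Protocol 9.1 sets no condition of importance or expectedness: "An adverse event is defined as any untoward medical occurrence in a patient or clinical investigation participant administered a pharmaceutical product". It adds a named group: "Incidences of hypotension, hepatitis (i.e. elevation of liver enzymes), and injection site reactions will be systematically collected and will be considered adverse events".

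Protocol 9.2 sets a separate rule for laboratory findings: "Changes in laboratory values will only be considered adverse events if they are judged to be clinically significant". It also allows an abnormality that fits a current diagnosis not to be counted. Protocol 9.3 lists respiratory, hepatic, renal, coagulation, central nervous system and vital-sign outcomes of the illness that are not adverse events, and makes a VDI rise of more than 33% from baseline an adverse event.

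The incidence of adverse events is a secondary safety variable in the Protocol Study Summary and a secondary objective in Protocol 4.2. It also appears in SAP Table 2. The SAP's adverse event section states: "All reported adverse events will be tabulated and categorized by level of severity and reported by treatment groups".

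**The concern.** Expectedness normally decides how fast an event is reported. In 9.0 it appears to decide whether the event goes on the form at all. The yardstick is the disease, so the events most exposed are those already common in these patients. A drug-related increase in such an event is hard to recognise in a single blinded patient and shows up mainly when the arms are compared. That comparison needs the events to be recorded whether or not each one was expected.

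The SAP tabulates reported events and cannot recover those never entered. The importance condition works the same way at the other end: the SAP classifies by severity, and minor events may be under-represented.

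The other safeguards are limited. The primary safety variable in the protocol, worst VDI, is hemodynamic only. Protocol 10.7 plans a safety look after 20 patients that is confined to VDI and hypotension. Protocol 11.4 states that no formal data safety monitoring board is planned. Harms outside hemodynamics and the safety laboratories therefore rest largely on the adverse event record.

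**Working it through.** The documents give no figure on this point, so the check is a comparison of the passages.

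**1. Which text says what goes on the adverse event form?** Only Protocol 9.0, and it names experiences that are both important and unexpected.

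**2. Which texts conflict with it?**
- Protocol 9.1: an adverse event is any untoward occurrence, with no filter.
- Protocol 7.2.3: adverse events are recorded in the CRF throughout the hospital stay, with no filter. Protocol 7.2.2 has a similar general statement.
- Protocol 9.5: routine collection from hour 0 to day 10, and later events also recorded if reported or observed.
- Protocol 9.0 itself: events that were not unexpected go to the IRB each year. That presupposes capture, but no form or data field is named.

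**3. Do those texts override the 9.0 rule?** No. Sections 7.2.2, 7.2.3 and 9.5 and the daily review row in Appendix A say when and for how long adverse events are recorded. They do not say which experiences qualify for the form.

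**4. Which events reach the adverse event data regardless of expectedness?**
- Hypotension, liver enzyme elevation and injection site reactions (9.1, repeated in the Study Summary and SAP Table 2).
- A VDI rise above 33% (9.3).
- Any event that the investigator or primary team suspects is drug-related (11.5).
- Laboratory changes judged clinically significant (9.2), although the allowance for abnormalities that fit a current diagnosis is close to an expectedness screen.

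**5. Which events are excluded by a different rule?** Renal failure, dialysis, raised creatinine, tachycardia and the other outcomes on the 9.3 list. Their absence comes from 9.3, not from the 9.0 sentence.

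**6. What is left?** Expected clinical events in neither step 4 nor step 5. An arrhythmia other than tachycardia is one example; it is this review's example, as the documents do not name it. Under 9.0 as written, such events can be left off the form at the investigator's judgement.

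**7. A related conflict.** 9.1 counts liver enzyme elevation as an adverse event, while 9.3 says hepatic injury or liver dysfunction is not one.

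**Illustration with assumed inputs.** Take 66 patients randomised 1:1, so 33 per arm. Assume that an event of the step 6 kind truly affects 20% of one arm and 40% of the other, with one episode per affected patient, and that a fraction f of episodes is left off the form, equally in both arms.
- Recorded rate = true rate × (1 − f).
- Recorded excess in patients = 33 × (0.40 − 0.20) × (1 − f) = 6.6 × (1 − f).
- f = 0: rates 20% and 40%, excess 6.6 patients.
- f = 0.8: rates 0.20 × 0.2 = 4% and 0.40 × 0.2 = 8%. Counts are 33 × 0.04 = 1.3 and 33 × 0.08 = 2.6, an excess of 1.3 patients.

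The excess falls in proportion to f, while the 2:1 ratio is unchanged. The documents supply neither the rates nor f.

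**The case against.** A reader might infer that only unexpected events are ever recorded, and that expected harms never reach the endpoint. The documents do not support that. The 9.0 sentence says what will be entered; it does not say that nothing else will be, and its annual-report provision implies that expected events are captured somewhere. Sections 7.2.2, 7.2.3 and 9.5 describe recording and collection without a filter, and Appendix A schedules adverse event review on each study day and at days 28 and 60.

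Nor do hypotension or renal decline illustrate the problem. Hypotension is collected systematically and has further routes through VDI and the 20-patient safety look. Renal outcomes are set aside by 9.3, and renal function is collected among the safety laboratories.

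It also goes too far to say that a between-arm excess is removed. Under a filter that acts equally in both arms, the excess shrinks and the ratio survives.

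The affected endpoint is secondary, the SAP's adverse event section plans tabulation without naming a test, and worst VDI does not depend on the form. Under 11.4, the safety officer reviews laboratory and clinical data daily.

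All of this stands and narrows the point. It does not remove it. The general statements do not define which experiences qualify, the annual report has no stated data source, and daily review of individual patients does not replace a comparison by arm. The route for suspected drug effects helps little with an event common in the disease, because few single cases will raise suspicion under blinding.

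**Conclusion.** The point holds as an inconsistency with a practical consequence. Section 9.0 ties form entry to a judgement of importance and unexpectedness that the 9.1 definition does not contain, and 7.2.3, 9.5 and the annual-report provision in 9.0 point the other way. If sites follow 9.0 literally, expected events outside the separately collected categories may be missing. The adverse event incidence may then be understated and a between-arm excess attenuated.

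The size cannot be computed from the documents. In the illustration, an excess of 6.6 patients per 33 falls to 1.3 if 80% of episodes are left off; the true rates, that fraction and its equality between arms are all assumptions. The conclusion also assumes that staff read the 9.0 sentence as the entry rule; if they apply 9.1 instead, little is lost. Because it affects a secondary endpoint and is cheap to correct, it should be changed. It does not bear on the primary efficacy analysis or on worst VDI.

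**What to change.** - **Protocol 9.0:** replace the form-entry sentence with a statement that all events meeting 9.1, other than those excluded under 9.2 and 9.3, are recorded on the adverse event form with severity, seriousness, relatedness and expectedness. State that expectedness governs expedited reporting only.
- **Protocol 9.3 and the SAP adverse event section:** state that the outcomes listed in 9.3 are still tabulated by arm, where available, from data already collected (for example laboratory values, oxygenation, ventilation status and vital signs).
- **Protocol 9.1 and 9.3:** reconcile the two statements on liver events, so that it is clear when a liver enzyme elevation is counted.

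The first change needs the second and third. Rewriting 9.0 without reference to 9.2 and 9.3 would create a new contradiction. The cost is protocol and SAP wording, somewhat more CRF entry and a few additional tables.

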9.1 Adverse Events

An adverse event is defined as any untoward medical occurrence in a patient or clinical investigation participant administered a pharmaceutical product that does not necessarily have to have a causal relationship with this treatment. An adverse event therefore can be any unfavorable and unintended sign (e.g., abnormal laboratory finding), symptom, or disease temporally associated with the use of an investigational product, whether or not the incident is considered to be related to the investigational product. Incidences of hypotension, hepatitis (i.e. elevation of liver enzymes), and injection site reactions will be systematically collected and will be considered adverse events.

9.2 Clinically Significant Laboratory Values

Any change in laboratory values will be evaluated. If a laboratory abnormality is new from baseline and thought to be clinically significant, it is considered a laboratory adverse event. However, if the laboratory value abnormality is consistent with a current diagnosis, it will not necessarily be considered an adverse event. Changes in laboratory values will only be considered adverse events if they are judged to be clinically significant (if some action or intervention is required or if the investigator judges the change to be beyond the range of normal fluctuation). Due to most of the urea cycle enzymes being hepatically located, elevation of liver enzymes will be systematically collected.

9.3 Pre-Existing Conditions

Pre-existing conditions that are present before the start of the study infusion will be considered concurrent medical conditions and should NOT be recorded as adverse events. However, if the subject experiences a worsening or complication of such a concurrent condition, the worsening or complication may be recorded as an adverse event at the discretion of the investigator.

The following are clinical outcomes of an acute hypoxemic respiratory illness progressing to critical illness due to COVID-19 infection (SARS-CoV2), and as such, will not be considered as adverse events:

1. Respiratory: decreased SaO₂/FiO₂ or PaO₂/FiO₂, mechanical ventilation, acute lung injury or acute respiratory distress syndrome (ARDS), or respiratory failure
2. Hepatic: hepatic injury or liver dysfunction; increased bilirubin
3. Renal: renal failure, need for dialysis, increased creatinine
4. Coagulation: disseminated intravascular coagulation (DIC), thrombocytopenia
5. Central Nervous System (CNS): acute mental status changes (not associated with localizing neurological signs)

6. Vital Signs: tachypnea, hypothermia, hyperthermia, tachycardia

Cardiovascular function will be systematically collected as both MAP and vasopressor dosages. VDI will be calculated at baseline (immediately before start of the infusion), again 60 minutes after completion of the bolus, and every 4 hours during the infusion. Any cases where the VDI increases by more than 33% from baseline will be considered an adverse event and submitted for review by the safety officer in an expedited fashion.

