**Table 2: Secondary Safety Endpoints**

Safety Variables:	

1. Primary safety variable is hemodynamic status, specifically worst vasopressor dependency index through day 10.

2. Incidence of reported adverse events.

Safety Evaluations:	
In addition to vasopressor dependency index, the following laboratory values will be used for safety assessment at baseline and daily through study day 4 when available.
 

1. Complete blood count with platelets

2. Basic Metabolic profile, including renal function

3. Liver function tests, including SGOT, SGPT, total bilirubin, and alkaline phosphatase

 
Adverse events will be recorded prospectively, including incidences of hypotension, hepatitis (i.e., the elevation of liver enzymes), and injection site reactions.

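### Protocol 9.1, 9.2 and 9.3 give three different rules on whether a liver enzyme rise is an adverse event, none takes precedence, and the SAP has no by-arm liver test summary to fall back on

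*Protocol*

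**What the plan says.** Protocol 9.1 names three events and makes them adverse events with no threshold, causality or significance condition: "Incidences of hypotension, hepatitis (i.e. elevation of liver enzymes), and injection site reactions will be systematically collected and will be considered adverse events".

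Protocol 9.2 sets a filter for laboratory findings in general: "Changes in laboratory values will only be considered adverse events if they are judged to be clinically significant". It adds a discretionary exception: "if the laboratory value abnormality is consistent with a current diagnosis, it will not necessarily be considered an adverse event". It then gives the reason for watching the liver: "Due to most of the urea cycle enzymes being hepatically located, elevation of liver enzymes will be systematically collected". That last sentence promises collection. It does not say that every rise is an adverse event.

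Protocol 9.3 lists outcomes of the illness progressing to critical illness, "and as such, will not be considered as adverse events". The hepatic line of that list reads "Hepatic: hepatic injury or liver dysfunction; increased bilirubin".

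Protocol 9.0 adds a further condition: experiences go on the adverse event form if they are clinically important and unexpected.

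The SAP repeats the named hepatic event in Table 2: "Adverse events will be recorded prospectively, including incidences of hypotension, hepatitis". Its method section for adverse events tabulates those that were reported, by severity and treatment group. Table 2 lists liver tests among the safety evaluations, but no SAP section describes a comparison or summary of post-baseline liver values by arm.

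**The concern.** Hepatic safety is something this protocol chose to watch. Enzyme elevation is one of three adverse events named in the Study Summary, in 9.1 and in SAP Table 2, and 9.2 ties it to the pathway on which the drug acts. A reader of the final report will look at the hepatic row of the adverse event table. If what enters that row depends on which section an investigator applied, the row cannot be reproduced from the source data and will tend to miss events.

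No other planned between-arm output covers the gap. The safety analysis after 20 patients (Protocol 10.7 and SAP Interim Analyses) concerns VDI and hypotension, not the liver. The liver test values are collected, but the SAP gives them no table.

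**Working it through.** The check is a comparison of texts. No sample size, power or alpha figure is involved, and the plan states no hepatic event rate to reproduce. I applied the rules to four cases.

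| Case | 9.1 | 9.2 | 9.3 | Result |
|---|---|---|---|---|
| A. Isolated ALT/AST rise, patient not progressing | Adverse event | Only if judged clinically significant | Not engaged | 9.1 and 9.2 differ when the rise is judged not significant |
| B. ALT/AST rise in a worsening patient, classed as hepatic injury or dysfunction | Adverse event | Depends on judgement; may be set aside as fitting a current diagnosis | Not an adverse event | Three different answers |
| C. Raised bilirubin alone, attributed to illness progression | The named-event sentence covers enzymes and does not reach it | Depends on judgement | Not an adverse event | No clash with the named event |
| D. ALT/AST rise suspected to be drug-related | Adverse event | Depends on judgement | No exception stated | Protocol 11.5 requires it to be reported; 9.0 has the safety monitor notified |

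Case B is the core of the point. Section 9.1 equates hepatitis with enzyme elevation, and 9.3 excludes hepatic injury. The two terms overlap, since an enzyme rise is an ordinary marker of hepatic injury. Section 9.3 has no exception for enzymes and no test for separating illness progression from other causes, while the 9.1 definition of an adverse event requires no causal link. The condition in 9.0 adds another reason to omit the event, because it too turns on judgement. None of 9.0 to 9.3 says which section prevails, and the SAP does not settle it.

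Case A shows a second, smaller conflict that a change to 9.3 alone would not remove: 9.1 is unconditional and 9.2 is not.

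Size. The gap between a count made strictly under 9.1 and one made under 9.3 is the number of patients in case B. The documents give no figure for it. What can be computed is the weight of one patient:

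- Up to 66 patients, 1:1: 66/2 = 33 per arm, and 1/33 = 3.0 percentage points.
- 60 patients, the number used for power: 60/2 = 30 per arm, and 1/30 = 3.3 percentage points.

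A few discretionary classifications are therefore enough to change how the hepatic row reads.

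**The case against.** The strongest reply is that the sections can be read together. The 9.3 list does not name ALT, AST or enzymes. It names bilirubin, as it names creatinine for the kidney, and it is confined to illness progression. On that reading, enzyme rises are in, and bilirubin and organ dysfunction from the disease are out. This is a coherent reading, but the protocol does not state it, and it leaves the clash between 9.1 and 9.2 untouched.

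A reader might infer more than the text supports, in four ways:

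- That 9.1, 9.2 and SAP Table 2 all make enzyme elevation an adverse event in every case. Only 9.1 does. Section 9.2 applies a significance filter, and Table 2 just names the event.
- That 9.1 and 9.3 disagree on every enzyme rise, so that recorded incidence could run from zero to the full rate. Case A lies outside 9.3, and no data in the documents support such a range.
- That the conflict hides a liver signal from the safety officer. Protocol 11.4 has that officer reviewing laboratory and clinical data daily, so enzyme values are visible whatever their classification. Protocol 11.5 also requires reporting of any event that the investigator or primary team is concerned may be drug-related.
- That the comparison between arms is biased or uninterpretable. Double blinding makes a systematic difference between arms unlikely. The expected fault is under-recording in both.

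These limits stand. They do not cure the count itself. Daily review works patient by patient and is not a comparison by arm, and the route in 11.5 depends on a blinded clinician suspecting the drug when the illness offers another explanation.

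**Conclusion.** The point holds as an inconsistency in recording rules. For an enzyme rise in a worsening patient that is classed as hepatic injury or dysfunction, the protocol permits both recording and omission, and the hepatic adverse event count is to that extent incomplete and not reproducible in both arms. Its effect on incidence cannot be estimated from the documents, beyond the roughly 3 percentage points that each reclassified patient carries.

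This rests on two assumptions: that clinicians would treat a notable enzyme rise as a form of hepatic injury, and that no CRF instruction outside these documents already fixes the rule. It is not a finding that individual patients go unmonitored or that a drug effect would be concealed. It deserves correction because the protocol itself singles out this signal and the correction is cheap.

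**What to change.** 1. Protocol: reconcile 9.0, 9.1, 9.2, 9.3 and 11.5 so that one stated rule decides when liver enzyme elevation is recorded as an adverse event. One way is an explicit carve-out for enzyme elevation in the hepatic line of 9.3, worded to agree with the significance filter in 9.2. Whichever rule is adopted, 9.1 and 9.2 must say the same thing.
2. SAP: add a by-arm summary of ALT, AST and bilirubin as shifts from baseline, taken from the laboratory data and produced regardless of adverse event status. State the days covered, because the Study Summary and SAP Table 2 speak of daily values through day 4, while Protocol 5.1.2 and Appendix A extend further.

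The cost is a short protocol edit and one SAP table, with no new procedures. If the protocol change comes too late for patients already treated, the table still helps. Its limit is that liver tests are standard-of-care values collected only when available, so the number of patients with data at each time should be shown.
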